#### Phase I open pilot study findings.

**Recruitment and screening.** Participants were recruited through community outreach, posting of IRB-approved flyers, and approaching patients at the Infectious Disease Clinic (BMC). At MGH, 19 participants were screened. 9 participants were eligible and were then consented/enrolled, although 3 of these participants were lost to follow up. At BMC, 20 participants were screened and 9 were eligible. Of these 9 participants, 4 were consented/enrolled and 5 were not consented due to lack of availability for group sessions and/or difficulty reaching via phone. 1 participant was lost to follow up due to over-commitment in research and scheduling difficulty.

**Feasibility and acceptability metrics.** 39 total participants were screened and 18 were found to be eligible (46.1%). Of these, 13 were consented/enrolled and 10 participated in the intervention (76.9%). The duration of the baseline assessment averaged 1.8 hours, ranging from 1.25 hours to 3.0 hours (N=13). Post-treatment assessments averaged 1.5 hours and ranged from 56 minutes to 1.57 hours (N=6). Exit interviews averaged 36.8 minutes and ranged from 12 minutes to 1.03 hours (N=6). Reasons for declining enrollment included work schedule, the number of group sessions, transportation cost and distance, medical reasons (e.g., surgical procedures limiting mobility), and other life circumstances. Of the 3 participants that were lost to follow-up, 2 noted that they were unable to participate due to medical reasons. Participants who have completed the intervention to date showed decreases in depressive symptoms as measured by the Center for Epidemiologic Studies Depression (CES-D) scale and increases in resiliency scores as measured by the Connor-Davidson Resilience Scale (CD-RISC). At the end of the intervention, participants reported being “very satisfied” with the program overall and stated that they would recommend it to others, although one participant noted the program was moderately burdensome as measured by the Perception of Study Assessments survey.

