**Study setting and participants.**

Participants will be recruited from the Boston-area hospitals and health care settings, including but not limited to MGH and MGH satellite clinics, Brigham and Women's Hospital, Boston Medical Center, as well as community organizations serving individuals living with HIV. The Infectious Disease clinic at MGH serves over 1,000 individuals living with HIV per year. Approximately 36% of female patients identify as White/Caucasian, 40% identify as Black/African-American, and 12% identify as Hispanic/Latina.

*Inclusion and exclusion criteria:*

We will recruit and enroll up to 60 individuals meeting the following criteria:

- (1) biologically born/cisgender women who endorse a female identity;
- (2) living with HIV
- (3) age 50 or over;
- (4) English speaking;
- (5) able and willing to sign informed consent.

We believe that non-cisgender women may experience unique and/or additional challenges than cisgender women (i.e., stigma related to sexual and/or gender identity, mode of HIV infection, etc.); thus, we have excluded them from the study at this time.

Exclusion criteria include: (1) presence of an active (i.e. untreated) and interfering psychiatric disorder (e.g., bipolar disorder, schizophrenia, substance abuse) that, in the opinion of the principal investigator or appropriate clinical staff, would compromise the individual's ability to participate in and benefit from the intervention; (2) have participated in structured cognitive behavioral therapy and/or a comprehensive mind-body intervention (including both mindfulness and behavioral therapy components) in the past year, also in the opinion of the principal investigator or appropriate clinical staff. By sampling from an array of medical centers, small clinics, and community organizations, we expect to recruit a representative sample of older women living with HIV.

If people are ineligible for the study at screening and ask for resources, we will refer them additional services in the community, including, but not limited to the following:

- (1) stress reduction groups at the Benson-Henry Institute for Mind Body Medicine at MGH;
- (2) mindfulness-based stress reduction and mindfulness-based cognitive therapy programs at the Center for Mindfulness at the University of Massachusetts Medical School;
- (3) "Find a Therapist" tool on the American Psychological Association website;
- (4) their primary care provider and/or their insurance company for a therapy referral

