Power calculations are based on samples of older, HIV-infected women when available. When data from older HIV-infected women were not available, data from samples of older women, women, or HIV-infected populations were used. We also examined data from community samples. We calculated power estimates for the primary outcome (resilience as measured by the CD-RISC) and for two of the secondary outcomes, depressive symptoms and health related quality of life. With respect to resilience, from Dodding et al., we estimate the standard deviation of change due to the intervention to be 11.8. With 30 patients per group, we will have 80% power to detect a change in resilience of 6.2 points or greater, in absolute value, based on a paired t-test at the 0.05 two-tailed significance level. We estimate the population mean and standard deviation to be approximately 76+/-13 for community-based controls, and 71.7+/-12.5 for a community-based sample of post-menopausal women with sub-clinical depression (N=401). A change of 6.2 points corresponds to approximately 1/2 of a standard deviation for both of these populations (i.e., an effect size of 0.5). Comparing the post-pre differences between treatment arms, we estimate that we will have 80% power to detect an absolute difference of 8.7 on the CD-RISC, based on a two-sample t-test at the 0.05 two-tailed significance level (an effect size of 0.7, which corresponds to a medium-large effect size.

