For depressive symptoms, Ickovics et al. reported that 42% of HIV seropositive women were depressed, based on reporting a CES-D score of >16 for 75% of more of study visits. Assuming that the population proportion of participants with elevated depressive symptoms in the placebo arm at the end of the study is 0.42, then with 30 participants per arm, we will have 80% power to detect that the corresponding treatment proportion is <0.12 or >0.76. For health related quality of life, Mrus et al. reported a mean for the overall health domain of HRQoL in women engaged in HIV treatment of 71.4, with a standard deviation of 13.8. Using this standard deviation, with 30 participants per arm, we will have 80% power to detect if the absolute mean between-group difference in this quality of life measure at the end of the study is 10.2 points or greater, based on a two-sample t-test at the 0.05 two-tailed significance level. In summary, we are confident that we can achieve a medium to large effect size across multiple outcomes with the proposed N.

**Analyses:** With respect to quantitative data, we will compare each outcome between groups using mixed- model regression analyses, with subject as a random effect. Fixed covariates will include time in study (baseline, end of treatment, 3 month follow-up) and time since diagnosis. Other covariates, such as education, socioeconomic status, and history of exposure to traumatic events will also be considered. We will consider exploratory mediational and moderational analyses, based on procedures outlined by Hayes. We will assess adherence in the active treatment arm, in particular to determine if adherence is related to change in the primary outcome. We will perform exploratory multivariate analyses among the outcomes, including graphical methods and the calculation and testing of correlations and partial correlations. We will examine patterns in missing data in order to see if missingness is related to measured patient characteristics. We will adjust for missing data using multiple imputation as appropriate. We will adjust for multiple comparisons using the method of Hothorn, Bretz and Westfall. Statistical analyses will be performed using “R” software.

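### The 80% power figures assume outcome data from 30 women per arm, which is the enrolment cap with no allowance for loss; with any realistic loss, power at the stated differences falls below 80%

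*Combined protocol and SAP*

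**What the plan says.** Under Statistical Plan for Analyses, the SAP gives four power statements, each at 80%.

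- CD-RISC change within an arm: "With 30 patients per group, we will have 80% power to detect a change in resilience of 6.2 points or greater", "based on a paired t-test at the 0.05 two-tailed significance level". The spread is given as "we estimate the standard deviation of change due to the intervention to be 11.8".
- CD-RISC change compared between arms: "we will have 80% power to detect an absolute difference of 8.7 on the CD-RISC", by a two-sample t-test. The 30 per group carries over from the preceding statement.
- Elevated depressive symptoms (CES-D): the proportion assumed "in the placebo arm at the end of the study is 0.42", against 0.12 or 0.76 on treatment, with 30 per arm.
- Health-related quality of life (HRQoL): "with 30 participants per arm, we will have 80% power to detect if the absolute mean between-group difference" is 10.2 points, with an SD of 13.8.

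On numbers, the protocol section on study setting and participants says "We will recruit and enroll up to 60 individuals meeting the following criteria". Study procedures specifies 1:1 randomisation. No loss rate or inflation factor appears in the power text or elsewhere; missing data appear only in the analysis text, which plans mixed models and multiple imputation.

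The Phase I findings in section 2.2 report 13 women enrolled, of whom 10 took part in the intervention (76.9%). The overall text counts 3 lost to follow-up. The site tallies count 3 at one site and 1 at the other, which leaves 9 of 13 (69.2%).

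**The concern.** All four calculations need an observed outcome: a post-minus-pre change, or status at the end of the study. They use the largest number that could be randomised as if it were the number analysed. Thirty is a ceiling, so losses can move power only downwards, and the team already had Phase I evidence that losses occur.

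What is at stake is how a null result is read. The SAP says the power work was done so that an absence of effect could not be put down to power, and it closes the power discussion by expressing confidence in medium to large effects across several outcomes. Neither statement is tied to an expected analysed number.

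**Working it through.** **Inputs.** Two-sided alpha 0.05. SD of CD-RISC change 11.8; HRQoL SD 13.8; control CES-D proportion 0.42 (all from the SAP). Cap of 60 randomised 1:1, so at most 30 per arm (protocol). Phase I retention 10/13 or 9/13 (section 2.2). The 27 and 25 per arm are assumed losses of 10% and about 17%. Loss is taken as equal in the two arms.

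**Formulas.**
- Paired t-test: noncentrality = (difference / SD) × √n, with n − 1 degrees of freedom.
- Two-sample t-test: noncentrality = (difference / SD) × √(n/2), with 2n − 2 degrees of freedom.
- For both, power is the chance that a noncentral t exceeds the two-sided 5% critical value.
- Proportions, unpooled: Φ(|p1 − p2| / √[(p1q1 + p2q2)/n] − 1.96). The pooled version uses the average proportion for the null variance.

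**Reproducing the SAP at n = 30.**
- Paired: 6.2/11.8 × √30 = 2.878 against a critical value of 2.045, giving 79.4%. The exact 80% difference is 6.24.
- CD-RISC between arms: 8.7/11.8 × √15 = 2.856 against 2.002, giving 80.2% (exact 8.68).
- HRQoL: 10.2/13.8 × √15 = 2.863 against 2.002, giving 80.4% (exact 10.15).
- CES-D 0.12 / 0.76: 79.4% / 81.4% unpooled, but 75.8% / 77.8% pooled. Of the methods tried, the unpooled variance comes closest to the stated 80%; the SAP names none.

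The SAP's figures are therefore correct for 30 analysed per arm, which confirms that they contain no loss.

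**Analysed numbers under Phase I retention.** 30 × 10/13 = 23.1; 30 × 9/13 = 20.8.

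**Power (%) at the stated differences.**

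| Analysed per arm | 6.2 paired | 8.7 between arms | HRQoL 10.2 | CES-D 0.12 / 0.76 unpooled | CES-D 0.12 / 0.76 pooled |
|---|---|---|---|---|---|
| 30 (no loss) | 79.4 | 80.2 | 80.4 | 79.4 / 81.4 | 75.8 / 77.8 |
| 27 (10% loss, assumed) | 74.8 | 75.8 | 76.0 | 75.1 / 77.2 | 71.1 / 73.2 |
| 25 (about 17% loss, assumed) | 71.3 | 72.4 | 72.6 | 71.9 / 74.0 | 67.6 / 69.7 |
| 23 (10/13 kept) | 67.3 | 68.6 | 68.8 | 68.3 / 70.5 | 63.8 / 65.9 |
| 21 (9/13 kept) | 63.0 | 64.5 | 64.7 | 64.3 / 66.5 | 59.6 / 61.7 |

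Losing one woman per arm (n = 29) already takes the three t-test figures to 78.0%, 78.8% and 79.0%.

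**Differences detectable with 80% power, n = 27 to 21.** HRQoL: 10.7 to 12.2 points. CD-RISC between arms: 9.17/11.8 = 0.78 to 10.46/11.8 = 0.89 SDs of change. CD-RISC within an arm: 6.61/11.8 = 0.56 to 7.58/11.8 = 0.64. The CD-RISC results are given in SD units for a reason. The protocol administers a 10-item version scored 0-40, whereas the SAP's reference means are 76 and 71.7, which that scale cannot reach. The power percentages depend only on the ratio of difference to SD, so they stand if 6.2, 8.7 and 11.8 share one scale.

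**Precision of 10/13.** The exact 95% interval is 46% to 95%. Thirty times those limits is about 14 to 28 per arm, or 47% to 77% power for the 8.7-point comparison.

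**The case against.** A reader might infer that the design actually delivers 63-69% power. The documents do not support that, for four reasons.

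- The 10/13 is the share who took part in the intervention, not the share with outcome data. Phase I reports six post-treatment assessments while describing its data collection as still under way, so it supplies no settled completion rate. The 9/13 rests on site tallies that disagree with Phase I's own total of 3 lost.
- Phase II is not a repeat of Phase I. The battery is shorter (45-60 minutes expected, against a 1.8-hour baseline average), the resilience-score entry criterion is gone, and make-up sessions, phone call-in and Zoom are available. Women who stop the intervention are still pursued for assessments, and those who cannot join a group after baseline may be re-consented and re-assessed for a later one.
- The interval for 10/13 is very wide.
- The planned analysis is a mixed model over three time points, so a woman seen only at 3 months still contributes. The calculations above, like the SAP's, are for t-tests.

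All four points stand, and they make the lower-power rows scenarios. They do not restore 80%, because 30 is the maximum and the plan does not quantify the retention it expects. Multiple imputation does not turn a woman with no post-baseline score into a full observation.

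It is also fair to say that efficacy is purely exploratory here, and that the SAP cites the funder's view that fully powered tests would be out of place. That rules out reading this as a case for a larger trial: holding 30 analysed per arm at 10/13 retention would need 30 ÷ (10/13) = 39 per arm, 78 in all, and nothing in the aims calls for it. Nor do the documents say that these power figures will be used to size the full-scale trial; they say only that Phase II data will inform it. But the exploratory status does not cover the SAP's assurance about null results, which is a claim about power.

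**Conclusion.** The point holds as an unstated assumption of no loss, not as an arithmetic error: the t-test figures are right for 30 analysed per arm. Power at the stated differences would be about 75-76% for the t-tests with 10% loss, 67-69% if 10/13 recurred, and 63-65% at 9/13. The CES-D comparison would have 68.3-70.5% at 23 per arm with the unpooled variance, or 63.8-65.9% pooled.

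These values rest on the SAP's SDs and control proportion, equal loss in the arms, and simple tests on women with outcomes. The direction is certain; the size depends on a retention rate that the documents do not establish. The primary feasibility and acceptability aim is unaffected. What cannot stand unqualified is the assurance that a null result would be unrelated to power.

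**What to change.** In the SAP's power text:

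1. Keep enrolment at up to 60. State an assumed loss with its rationale, and the expected analysed number per arm. If Phase I is cited, say that 10/13 is participation in the intervention, and reconcile it with the site tallies.
2. Replace the single 80% statements with power, or detectable differences, over about 21 to 27 analysed per arm. For HRQoL the detectable difference is about 10.7 to 12.2 points. For CD-RISC between arms, give 0.78 to 0.89 SDs of change until the 0-40 instrument and the SAP's reference values are reconciled; do not insert new point values before then. Say that the divisor is the SD of change (11.8), since the SAP's effect size of 0.7 for 8.7 points is close to 8.7/12.5 and 8.7/13, its population SDs, whereas 8.7/11.8 = 0.74.
3. Recompute the CES-D statement at the same analysed numbers and name the test and variance used.
4. Qualify or withdraw the assurance that a lack of effect would be unrelated to power.

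The cost is wording only. The stated figures become less favourable; no participants, visits or analyses are added.

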#### Resilience.

*Resilience:* The Connor-Davidson Resilience Scale (CD-RISC) is a self-report measure of resiliency comprised of 10 items rated on a five-point scale (0 = not true at all, 1 = rarely true, 2 = sometimes true, 3 = often true, 4 = true nearly all the time). Items capture various aspects of resilience including adaptability to change, availability and use of social support, and problem-solving style. Total scores range from 0-40; high scores indicate greater resilience. The CD-RISC has demonstrated good psychometric properties in previous research, including among medical populations.

*Measure of Current Status (MOCS-A):* The MOCS-A is a 13-item self-report measure of stress reactivity and coping, which will be administered at baseline and post treatment. It was developed to assess one's current self-perceived status on several skills targeted by the intervention, including the ability to relax at will, recognize stress-inducing situations, restructure maladaptive thoughts, be assertive about their needs, and choose appropriate coping responses. Statements are rated from 0 (I cannot do this at all) to 4 (I can do this extremely well). Scores range from 0-52; higher scores suggest better coping skills.

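### The power paragraph benchmarks the CD-RISC against means of 76 and 71.7, which the 10-item, 0–40 form described in the protocol cannot produce

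*Combined protocol and SAP*

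**What the plan says.** The protocol, under Assessment instruments (Resilience), describes the CD-RISC as "comprised of 10 items rated on a five-point scale", with response options from 0 to 4, and adds: "Total scores range from 0-40; high scores indicate greater resilience". The item count and the range agree with each other.

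The SAP, under Statistical Plan for Analyses (Power), calculates power for resilience on the CD-RISC without naming a version:

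- Variability: "we estimate the standard deviation of change due to the intervention to be 11.8".
- Within-arm result, paired t-test: "we will have 80% power to detect a change in resilience of 6.2 points or greater", with 30 per group.
- Benchmarks: "We estimate the population mean and standard deviation to be approximately 76+/-13 for community-based controls", and "71.7+/-12.5 for a community-based sample of post-menopausal women with sub-clinical depression".
- Interpretation: "A change of 6.2 points corresponds to approximately 1/2 of a standard deviation for both of these populations", which the SAP labels an effect size of 0.5.
- Between-arm result, two-sample t-test: "80% power to detect an absolute difference of 8.7 on the CD-RISC", labelled an effect size of 0.7.

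Neither section mentions a second version of the scale, a rescaled total or a conversion.

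**The concern.** A score that cannot exceed 40 cannot have a mean of 76 or 71.7. The benchmarks are not incidental background, because the SAP uses their SDs to interpret its power result. If the SD of change of 11.8 comes from the same wider-ranging score, the 6.2- and 8.7-point figures are in the wrong units for the form to be administered.

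Two uses of these figures are at stake. The SAP says power was calculated so that a null finding could not be put down to low power, and that claim needs detectable values in the units of the score analysed. The Specific Aims say the data will inform a full-scale trial, so a reader could carry 6.2 or 8.7 forward as points on a 0–40 scale.

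**Working it through.** **Inputs.** From the protocol's Resilience section: 10 items, each 0–4. From the SAP's power paragraph: SD of change 11.8; 30 per group; 80% power; two-sided 0.05; benchmarks 76 ± 13 and 71.7 ± 12.5; stated effect sizes 0.5 and 0.7.

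**1. Reproduce the stated figures.** Noncentral t, solved for the standardised difference d at 80% power:

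- Paired, n = 30 (29 df): d = 0.529; 0.529 × 11.8 = 6.24 points (stated 6.2).
- Two-sample, 30 per arm (58 df): d = 0.736; 0.736 × 11.8 = 8.68 points (stated 8.7).

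Power at exactly 6.2 and 8.7 points is 79.4% and 80.2%. The arithmetic is sound.

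**2. Range check.** The maximum total is 10 × 4 = 40. The benchmark means exceed it by 76 − 40 = 36 and 71.7 − 40 = 31.7. At 4 points per item, a mean of 76 needs at least 76 / 4 = 19 items.

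**3. Where the effect-size labels come from.**

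| Difference | ÷ 13 | ÷ 12.5 | ÷ 11.8 |
|---|---|---|---|
| 6.2 | 0.48 | 0.50 | 0.53 |
| 8.7 | 0.67 | 0.70 | 0.74 |

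The stated 0.7 fits the benchmark SDs and not 11.8, so the labels are in population-SD units taken from the out-of-range score.

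**4. The scale of 11.8.** It is not stated. An SD of change of 11.8 is arithmetically possible on 0–40, but the SAP treats the 6.2 points derived from it as being in the same units as the SDs of 13 and 12.5. The likelier reading is therefore that 11.8, 6.2 and 8.7 are all on the wider scale.

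**5. Detectable values on a 0–40 score.** The documents give no SD of change for the 10-item form, so these SDs are assumptions for illustration:

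| Assumed SD of change | Within arm (0.529 × SD) | Between arms (0.736 × SD) | Power at 6.2 / 8.7 points |
|---|---|---|---|
| 4 | 2.1 | 2.9 | >99.9% / >99.9% |
| 6 | 3.2 | 4.4 | >99.9% / >99.9% |
| 8 | 4.2 | 5.9 | 98.4% / 98.5% |
| 10 | 5.3 | 7.4 | 91% / 91% |
| 11.8 (as stated) | 6.2 | 8.7 | 79.4% / 80.2% |

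If 11.8 came from a 0–100 score and shrank in proportion (also an assumption), the SD would be 11.8 × 0.4 = 4.72, giving about 2.5 and 3.5 points.

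**6. Whether the labels carry over.** They hold for the 10-item form only if the ratio of change SD to population SD stays near 11.8/13 = 0.91 to 11.8/12.5 = 0.94. With equal pre and post variances the ratio is √(2(1 − r)), where r is the pre–post correlation. Multiplying 0.529 and 0.736 by it gives:

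- r = 0.3: ratio 1.18, labels 0.63 and 0.87
- r = 0.5: ratio 1.00, labels 0.53 and 0.74
- r = 0.7: ratio 0.77, labels 0.41 and 0.57

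**The case against.** The contradiction itself has no good answer, but its reach can be disputed.

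- **Little depends on it.** The Specific Aims call these analyses exploratory, feasibility and acceptability are primary, no decision rule uses the figures, and the SAP also supports its sample size by comparison with similar funded studies. All of this stands and limits the importance of the point. It does not make the paragraph correct, and the same paragraph calls resilience the primary outcome.
- **A minimum detectable difference is not a measure's responsiveness.** This is true: it depends on n, alpha and the SD, whereas the plan's interest in sensitivity to change will be judged from the trial data. But the SAP gives its own reason for calculating power, to exclude low power as the cause of a null result, and that reason needs the right units.
- **The documents never name a longer CD-RISC.** A rescaled total would also explain 76 and 71.7. This stands: what is certain is a different score range, and the scale of 11.8 is an inference. If 11.8 is in fact on 0–40, the 6.2 and 8.7 points are right and only the benchmarks and the 0.5 and 0.7 labels fail.
- **The illustrative SDs have no source in the documents.** This also stands. The power of at least 98% applies up to an SD of 8; at 10 it is about 91%. The direction is the same for any SD below 11.8.
- **Thirty per arm is the enrolment ceiling.** In Phase I, 10 of 13 enrolled women took part. At that rate about 23 per arm would be analysed (30 × 0.769), and the detectable values would be 0.61 and 0.84 SD. That is a separate matter from the scale, but replacement text should say that 30 means analysed.

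**Conclusion.** The inconsistency holds. It is certain that the form described in the protocol cannot yield the SAP's benchmark means, and that the 0.5 and 0.7 labels rest on SDs from a score with a different range. It is probable, not certain, that 11.8, 6.2 and 8.7 are also on that score. On either reading the power paragraph needs correction for the 10-item form.

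Sample size and detectability in SD-of-change units (0.53 within arm, 0.74 between arms) do not change. If 11.8 is on the wider scale and the SD of change on 0–40 is smaller, the stated point values overstate the smallest detectable change, so the error is conservative. The protocol's summary of Phase I changes reports a shortened assessment battery. That would fit power text left un-updated, but it does not name the CD-RISC and proves nothing. The point is worth correcting and its consequence is limited.

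**What to change.** Reconcile the protocol's Resilience section with the SAP's power paragraph, and state in the SAP the CD-RISC version, its score range and the scale on which 11.8 was measured.

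**If the 10-item form stands:** remove the benchmark means and SDs and the 0.5 and 0.7 labels. Remove 6.2 and 8.7 as well, unless 11.8 is shown to be on the 0–40 scale. Replace them with values from a sourced SD of change for that form or, if none is available, with a sentence such as:

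> With 30 participants analysed per arm, we have 80% power to detect 0.53 SD (within arm) and 0.74 SD (between arms) of the change score.

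**If a longer form or a rescaled total is in fact used:** correct the protocol's description of the items and score range accordingly, and keep the SAP figures with the version and scale added.

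The cost is wording in one or both sections, plus one recalculation if a sourced SD is found. Sample size, design and conduct do not change.
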